These follow-up visits are standard of care. The tests are standard physical assessments done by the neurologists, and no specific interventions will be made for the study. Our study team will review EMR to obtain results/notes.

5) Subjects will be instructed to return to the emergency department if their condition is worsens or if they develop new neurological symptoms.

6) In addition to the clinic data, as standard of care, patients will have an MRI of the brain performed during the first 48 hours of their hospital admission and a follow-up MRI of the brain at 3 months as part of the standard of care for stroke patients. As per standard neurology evaluation, a blood test for s100b, neuronal specific enolase level will be obtained by the neurology team while the subject is admitted. MRI data will be analyzed initially for the type of stroke (either embolic, or thrombotic), stroke associated edema, for volumetric changes at three months poststroke, and gliosis at three months.

7) Telephone contact will be attempted if a subject is transferred to an outside hospital following admission, or if a subject does not show up to clinic for re-evaluation as scheduled, and efforts will be made to evaluate the patient in the time allotted. We will make a maximum of 3 phone calls within a 1 week period.

a) Inclusion and Exclusion Criteria

Inclusion Criteria:

Consecutive subjects between ages 18 years or older evaluated in the emergency department at Harbor-UCLA Medical Center with signs and symptoms of acute ischemic stroke presenting within 24 hours of symptom onset. Individuals must have a NIHSS of at least 5 to be included. All individuals regardless of gender or race will be included. For adults who cannot consent for themselves because of the severity of their stroke, one of the investigators will offer participation in the study to the family member who possesses the authority for medical decision making for the patient. There is no financial incentive for either the patient or the investigator. It will also be explained that the potential benefit of giving N-acetylcysteine is unknown and that the patient will receive excellent care (standard for their presentation) whether they participate or not and outside of not receiving the study drug.

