Our patients tend to be economically disadvantaged but since there are no financial incentives either for the patient or for the investigators, this bias has been minimized. Patients will receive the same care whether they participate in the study or decline.

Exclusion Criteria:

- Evidence of hemorrhagic stroke on initial CT scan
- Need for thrombectomy as determined by the treating neurologist
- Known allergy to NAC
- Protected populations, including age < 18, known pregnancy, and prisoners
- Patients who are DNR/DNI at the time of presentation with a short life expectancy

b) Local Number of Subjects

The total number of local subjects will be 117 (39 subjects with moderate stroke = NIHSS 5-15; 39 subjects with moderate to severe stroke = NIHSS 16-20; 39 subjects with severe stroke = NIHSS = 21-42)

This number was derived using a group size analysis based on previous work on oral NAC for ischemic stroke (37) and a hypothesis of finding no

difference (defined as a change in NIHSS < 4) between NIHSS scores at 90 days. With a power of 0.80 and an alpha 0.05 we would need 47 subjects in each group. Assuming a dropout rate of 25% or lost to follow-up, we would enroll 59 in each group for a total of 117.

(Group sample sizes of 47 and 47 achieve 81% power to detect a difference of 4.0 using a one-sided Mann-Whitney U or Wilcoxon Rank-Sum test assuming that the actual data distribution is normal when the significance level (alpha) of the test is 0.05 and the standard deviation is 7.4 in both groups.)

c) Study-Wide Number of Subjects

This is a single center study at the Harbor-UCLA Medical Center.

d) Study Timelines

Estimated time to complete enrollment is December 2025. Review of the neurology services revealed that Harbor-UCLA typically sees 20 patients per month that would be eligible for the study.

e) Study Endpoints

The primary study endpoint will be comparison between groups (NAC treated group versus treatment) of the NIHSS at 90 days.

Secondary endpoints include changes in the MRS, GOS, BI, and blood tests at 30 days and 90 days, as well as MRI data including changes in brain volume and gliosis at 90 days.

f) Procedures Involved in the Human Research

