All subjects would then be admitted to the Neurology Service to either an Intensive Care Unit bed or a Step-down intensive care unit bed.

Subjects will return to neurology clinic on days 30 and 90 and undergo reevaluation by a neurology resident using the same assessments performed on day 0. Data will be collected on a standard data collection sheet at each visit. In addition, the subjects will undergo the following two assessments:

Glasgow Outcome Scale (GOS, follow-up visits only):

GOS is a 5-point scale on which 1- death, 2- persistent vegetative state, 3- severe disability, 4- moderate disability, and 5- low disability.

Barthel Index (BI, follow-up visits only):

BI evaluates the ability to perform activities of daily living, on a scale that ranges from 0 to 100. Activities assessed include: presence or absence of fecal incontinence, presence or absence of urinary incontinence, help needed with grooming, with toilet use, with feeding, with transfers, with walking, with dressing, with climbing stairs, and with bathing.

These follow-up visits are standard of care. These tests are standard physical assessments done by the neurologists, and no specific interventions will be made for the study. Our study team will review EMR to obtain results/notes.

5. Each patient will complete two separate MRI's of the brain, which are both standard of care. The MRI's are considered standard of care and will not be different in acquisition than MRI's currently obtained for stroke patients. We will use software packages available to post-process these images for research purposes as outlined in the protocol.

6. Patients will have a "stroke panel" of lab tests as mentioned above, which are the standard of care at our facility. The total amount of blood obtained for the entire duration of the study will be less than 100ml.

7. We will also pre-define a per-protocol (excluding Stroke Mimics as defined as a negative brain MRI obtained within 2 weeks of the onset of symptoms) versus an intent to treat protocol. This would allow for the loss of study subjects who might stop the NAC after a negative MRI who are no longer thought to have had a Stroke.

g) Data and Specimen Banking

No specimens will be stored.

Data Collection sheets will be utilized for initial assessment and follow up. See attached documents.

h) Data Management

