assessment. This will be an open-ended question that will be recorded prospectively for each subject. If the subject reports an adverse event this is still present at the time of the phone call and wants to be further evaluated, they will be asked to return to the emergency department and seen by a physician not associated with the investigation. Further the investigator from the team will also meet them in the Emergency Department to detail the information. All adverse events, whether they are deemed mild or serious, will be forwarded immediately to the Medical Monitor who can immediately halt or terminate the study. In addition, all adverse events will be reported to the IRB of the Lundquist Institute by the investigators (and independently by the Medical Monitor). In a written IND safety report, any adverse experience associated with the use of the drug that was both serious and unexpected will be immediately reported to the FDA.

Definition of adverse events for this protocol:

Adverse Events

Symptoms that are new or unexpected reported by the subject

Nausea, diaphoresis, chest pain, abdominal pain, paresthesias, headache, visual complaints

Cough, pruritis, rash

Laboratory abnormality

Minor bleeding from gums, nares

Mild Sedation

Serious Adverse Events

Significant adverse events that led to an intervention, including withdrawal or dose reduction in the investigation drug or the need for concomitant therapy

Wheezing, bronchospasm, angioedema requiring rescue medications

Bleeding requiring an intervention

Hemorrhagic conversion of the ischemic CVA

Worsening neurologic condition as measured by the NIHSS at 4 hour intervals after enrollment in the study (or sooner as dictated by the care of the neurology team)

Laboratory abnormality requiring intervention (e.g. severe hyponatremia or hyperkalemia)

Death

k) Withdrawal of Subjects

Subjects will be withdrawn if they leave AMA/elope during their initial hospitalization or do not complete their 30 day or 90 day follow up prior to completion of the study

11) Risks to Subjects

Risk of N-Acetylcysteine:

Most adverse drug reactions that have been reported are minor and easily managed. Serious anaphylactoid reactions are extremely rare (11, 33-36)

Common: Nausea, vomiting, flushing, and pruritus,

Uncommon: Wheeze and bronchospasm (7.1%) Rare:

Angioedema, and hypotension (25-28)

Risks of Diphenhydramine

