Consent process will take place in the emergency department, ensuring subject privacy away from other on-going activities and personnel. The standard operating procedure for informed consent will be followed (SOP: Informed Consent Process for Research, HRP-090). Investigators or HIPPA trained research associates will seek consent for participation in this study from patients, their next of kin, or their legally authorized representative. The study will be explained during an approximately 15 minute discussion with the patient or their representative. They will be given as much time as they want to decide whether to participate in the study. The informed consent process requires that patients, their next of kin, or their legally authorized representative must be able to understand, retain, and repeat the purpose, risks and benefits of the study to the consenting physician. Participants will be reminded that participation in the study is voluntary and their questions, if any, will be answered. All participants will be immediately withdrawn from the study if they appear to be unduly distressed. If subject requires some time for the information to be absorbed and appreciated, the researcher allow a period of time to elapse between imparting the information and requesting a signature on the consent form.

Non-English Speaking Subjects

Other than English, we expect Spanish speaking population to be participated in the study. In such case, consent form written in Spanish will be provided, and we will provide oral information using language line or by Spanish speaking investigators.

Subjects who are not yet adults (infants, children, teenagers) Only subjects over the age of 18 will be included in this study.

Cognitively Impaired Adults & Adults Unable to Consent

Stroke victims may have cognitive impairment and lack capacity to provided informed consent. The study team will assess each patient's capacity for decision-making using a post consent survey (Appendix 1: Decision-Making Evaluation Form) and decision tree/flow diagram (Appendix 2).

Some stroke victims may be able to understand and communicate their willingness to participate but unable to physically sign a consent document. In these instances, we will seek permission/consent from their legally authorized representative for participation and seek the subjects “assent” (verbal) for participation as they are deemed able.

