If subject is deemed incapable of decision-making or unable to physically sign a consent document, consent will be sought from the subject’s the Legally Authorized Representative (as per HRP-013 SOP LARs, Children, Guardians). This individual will complete the Self-Certification of Surrogate Decision Makers form (Appendix 3) for documentation.

Study participation will be discussed with both the patient and the physician of record/primary medical providers. Patient capacity to make decisions will be determined by the primary medical providers per routine. The study team will also determine each patient’s (potential subject’s) decision making capacity for participation in the study. Patients without capacity to make decisions and who lack a surrogate decision maker will be excluded from the study. Surrogate decision makers will be informed about the study in the same way as described above and offered to provide consent for the patient to enroll in the study.

If and when a subject regains their capacity for decision-making, consent for continued participation in the study will be sought. The standard operating procedure for informed consent will be followed (SOP: Informed Consent Process for Research, HRP-090).

17) Process to Document Consent in Writing

We are following “SOP: Written Documentation of Consent (HRP-091).”

Individuals who are not yet adults, pregnant women, and prisoners will be excluded in this study. Other vulnerable subjects, such as students, subjects with limited or no treatment options, and socially and economically disadvantaged, may be included in this study. This study does not involve more than minimal risk to the subject.

18) Drugs or Devices

N-Acetylcysteine and placebo. Study drugs will be stored, handled and dispensed by an ED pharmacist who is working at the time of study enrollment.

[name]., the ED Pharmacist will maintain drug accountability logs in compliance with FDA regulations. She will instruct other ED pharmacists about the study and the randomization log which will

be kept in the pharmacy room in the ED. She will also create study drug labels to keep the nurses, physicians and patients blinded to the study medication.

19) Multi-Site Human Research

N/A

20) Community-Based Participatory Research

This is not a community-based participatory research project.

21) Sharing of Results with Subjects

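### Section 10(k) withdraws randomised subjects whose day-90 NIHSS could still be obtained, and the text available neither says who is in the intent-to-treat set nor places death in the primary comparison

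*Combined protocol and SAP*

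**What the plan says.** Section 10, item 3 randomises subjects thirty minutes after enrollment. Section 10(k) then sets the withdrawal rule: "Subjects will be withdrawn if they leave AMA/elope during their initial hospitalization or do not complete their 30 day or 90 day follow up". The clause continues, so that the visit trigger in full concerns subjects who "do not complete their 30 day or 90 day follow up prior to completion of the study".

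The day-30 and day-90 visits are described as standard of care, and the outcome is read from the chart: "Our study team will review EMR to obtain results/notes" (sections 10 and 10(f)). For a subject who is transferred or misses a visit, section 10, item 7 provides up to three calls within a week and says "efforts will be made to evaluate the patient in the time allotted".

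On analysis sets, section 10(f), item 7 defines a per-protocol set that leaves out stroke mimics and contrasts it with the words "versus an intent to treat protocol", without more. On the endpoint, section 10(e) states: "The primary study endpoint will be comparison between groups (NAC treated group versus treatment) of the NIHSS at 90 days". The protocol gives death a value of 6 on the MRS and 1 on the GOS. Its NIHSS bands end at 42, with no category for death.

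Section 16, on adults unable to consent, adds a further exit after enrollment: "If and when a subject regains their capacity for decision-making, consent for continued participation in the study will be sought".

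**The concern.** Withdrawal under section 10(k) is triggered by what happens after randomisation, and such events can depend on how the subject is doing. If withdrawn subjects drop out of the day-90 comparison, the arms compared are no longer the arms randomised. Losing more of the worst subjects on NAC would flatter NAC. Losing fewer of them, for instance because lives are saved, would hide a benefit.

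A subject who dies before day 90 has, read literally, also failed to complete follow-up and so falls under the same rule. Death is a foreseeable event here: it is listed as a serious adverse event, and 39 + 39 = 78 of the 117 places are for NIHSS 16 to 42.

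A route to loss that differs by arm also exists. Section 10(j) unblinds the treating physician for serious adverse events, which include neurologic worsening. That this would lead to unequal loss is an inference, not a documented rate.

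**Working it through.** **Reading the rule.**

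- *Leaving against medical advice.* Unambiguous: the subject is withdrawn. Nothing about leaving the first admission prevents an NIHSS at a day-90 clinic visit.
- *Missed visits.* The second "or" in the rule can mean either visit missed or neither completed. On the first reading, a subject examined at day 90 who missed day 30 is withdrawn with the primary outcome in hand. On the second, only subjects with no follow-up are withdrawn. The first reading also sits badly with section 10, item 7, which tries to recover subjects after a missed visit.
- *Intent-to-treat.* No available text says whether withdrawn subjects belong to the set, or what is done when the day-90 NIHSS is missing.

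**Reproducing the plan's power (section 10(b)).** Inputs: 47 per group, difference 4.0, SD 7.4, one-sided alpha 0.05, Mann-Whitney test. With the rank test's efficiency 3/π under normality, the effective n is 47 × 3/π = 44.9. The standardised difference is 4 / (7.4 × √(2/44.9)) = 2.56, and Φ(2.56 − 1.645) = 0.82. Simulation gives 81 to 82%. The plan states 81%, so it reproduces. At the plan's 25% loss, 117 × 0.75 = 87.75 subjects remain, about 44 per arm, with power near 80%.

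**Illustrating the bias.** The documents give no loss by arm, no mortality and no link between loss and severity, so these are assumptions. Take 58 per arm (117/2, rounded down). Latent day-90 severity is z, and a subject is lost when ρz + √(1 − ρ²)·noise exceeds the cut-off c that gives the stated loss p. Only completers are compared, by the one-sided Mann-Whitney test.

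The mean of z among those kept is −ρ·φ(c)/(1 − p):

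- 20% loss: 0.280/0.80 = 0.350
- 30% loss: 0.348/0.70 = 0.497

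With 20% lost on placebo and 30% on NAC (12 and 17 subjects, together about the 29 that 25% of 117 implies), the spurious difference is −ρ × 7.4 × (0.497 − 0.350) = −1.09ρ NIHSS points. At ρ = 0.5 that is about 0.5 points in favour of NAC; at ρ = −0.5 it is about 0.5 points against.

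False-positive rate with no true effect (simulation):

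| Loss, placebo v NAC | ρ = −0.5 | ρ = 0 | ρ = 0.5 |
|---|---|---|---|
| 25% v 25% | about 5% | about 5% | about 5% |
| 20% v 30% | about 2% | about 5% | about 9% |

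The opposite imbalance hides benefit. With a true 4-point shift and ρ = 0.5, completer power is about 83% at 25% loss in both arms and about 72% at 30% on placebo v 20% on NAC.

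The equal-loss result depends on the loss model. If exactly the sickest 10% of each arm are removed, the rate is about 7% instead of 5%.

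**The case against.** The strongest reply is that section 10(k) never says data are discarded or that anyone leaves the analysis. With its reference to study completion, the visit clause may only describe loss to follow-up, for which section 10(b) already allows 25%. That stands, and it limits the point: the loss is possible rather than planned, and intent-to-treat is left undefined rather than made impossible. It does not answer the clause on leaving against medical advice, or the absence of any text keeping such subjects in follow-up.

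A reader might infer that the plan has no definition of intent-to-treat and no death rule anywhere, and therefore compares survivors only. The documents do not support that. The end of the file, from within the bibliography on, was not available, and no available passage says deaths are omitted.

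A reader might also take loss to mean loss of the worst cases. Subjects who leave early may be milder, and then the test becomes conservative, as the ρ = −0.5 column shows. Larger false-positive rates, near 26%, appear only if loss is perfectly tied to severity and also differs by ten percentage points between arms. The documents support neither assumption.

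Finally, section 16 says: "All participants will be immediately withdrawn from the study if they appear to be unduly distressed". This could be read as another exit after randomisation. It sits within the description of the consent conversation, just before the sentence on allowing time before signature, and most naturally concerns distress before randomisation. It merits a query at most.

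**Conclusion.** The point holds on the wording. Section 10(k) withdraws randomised subjects who leave against medical advice and, on one reading, those who miss only day 30, although the primary outcome may be obtainable from a visit the protocol calls standard of care. That rule should change whatever the missing pages contain. The intent-to-treat definition and the place of death in the day-90 NIHSS comparison are to be confirmed or added.

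The size is unknown. Under the assumed 20% v 30% loss, the nominal 5% test runs at about 9% or about 2%, depending on the sign of a correlation that the documents do not give. With equal loss and the threshold model it stays near 5%. The case for acting is that the result should not rest on loss being balanced, or on a choice of analysis set made after unblinding.

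It does not follow that death must be ranked worst. That is one defensible rule among several, and it has a cost in power.

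**What to change.** 1. **Section 10(k).** Stop treating departure against medical advice, or a missed day-30 visit, as withdrawal from the study. State that every randomised subject is followed to day 90 by clinic visit, medical record or the calls in section 10, item 7, unless consent for follow-up is withdrawn, and that data already collected are kept. This concerns follow-up and analysis, not treatment.
2. **Section 10(f), item 7.** Define intent-to-treat as all randomised subjects by assigned arm, or point to existing text that does so.
3. **Section 16.** Say whether declining to continue when capacity returns ends record-based follow-up, and count these refusals by arm. Clarify whether the distress sentence applies only during consent.
4. **Section 10(e).** Before unblinding, name one rule for death and one for unknown vital status in the primary comparison, or point to existing text. For unknown status, one option is to count unknowns as dead in one arm and alive in the other, then reverse. Report deaths by arm and the day-90 MRS beside the primary result.
5. **Section 10(b).** Restate the power under the chosen rule, and say whether the 25% includes deaths.

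**Cost.** Items 1 to 3 need wording and some tracing effort, with no new visits. The death rule may lower the stated power. For example, if NAC shifts NIHSS by 4 points without changing mortality, and death has correlation 0.5 with severity, ranking death worst at 58 per arm takes power from 87% to 76% at an assumed 10% mortality, from 86% to 68% at 15%, and from 84% to 59% at 20%. About 80% power would then need roughly 66, 80 or 100 per arm. The sponsor may enlarge the trial, accept and state lower power, or choose another rule.
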